8.2.3 Expectedness

As this study is minimal risk, no adverse events are expected.

8.3 Time Period and Frequency for Event Assessment and Follow-Up

The occurrence of an AE or SAE may come to the attention of study personnel during study visits and interviews of a study participant presenting for medical care, or upon review by a study monitor. All AEs including local and systemic reactions not meeting the criteria for SAEs will be captured. Information to be collected includes event description, time of onset, clinician's assessment of severity, relationship to study intervention (assessed only by those with the training and authority to make a diagnosis), and time of resolution/stabilization of the event. All AEs occurring while on study must be documented appropriately regardless of relationship. All AEs will be followed to adequate resolution.

Any medical condition that is present at the time that the participant is screened will be considered as baseline and not reported as an AE. However, if the study participant's condition deteriorates at any time during the study, it will be recorded as an AE. UPs will be recorded in the data collection system throughout the study.

Changes in the severity of an AE will be documented to allow an assessment of the duration of the event at each level of severity to be performed. AEs characterized as intermittent require documentation of onset and duration of each episode.

The PI will record all reportable events with start dates occurring any time after informed consent is obtained until 7 (for non-serious AEs) or 30 days (for SAEs) after the last day of study participation. At each study visit, the investigator will inquire about the occurrence of AE/SAEs since the last visit. Events will be followed for outcome information until resolution or stabilization.

All unresolved adverse events should be followed by the investigator until the events are resolved, the subject is lost to follow-up, or the adverse event is otherwise explained. At the last scheduled visit, the investigator should instruct each subject to report any subsequent event(s) that the subject, or the subject's personal physician, believes might reasonably be related to participation in this study. The investigator should notify the study sponsor of any death or adverse event occurring at any time after a subject has discontinued or terminated study participation that may reasonably be related to this study.

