7.3 Study Schedule

7.3.1 Screening

Recruitment (within three months of enrollment)

- Review self-reported medical history to determine eligibility based on inclusion/exclusion criteria.
- Conduct preliminary MRI safety screen.
- If potential participant meets eligibility criteria by self-report and wishes to enroll, notify that we will schedule enrollment visit (TP0) once a potential group of participants is formed. The potential participant will have the opportunity to decline participation again at that point.

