7.3.5 Final Study Visit (Visit 13)

TP2 (long-term follow-up assessment within three months [+/- 1.5 weeks] of completion of intervention)

- Confirming that eligibility criteria have not changed since TP1 assessment.
- Collect 15 ml (1 tablespoon) of blood for biobanking.
- Obtain any changes in demographic information, medical history, medication history, and alcohol and tobacco use history.
- Assess for any adverse events, serious adverse events, or unexpected problems.
- Complete patient-reported outcome measures.
- Complete neuropsychological testing.
- Complete study assessment questionnaire.

CONFIDENTIAL

- Complete final REDCap diary.
- Notify participant that aggregate-level results will be available after dissemination of study findings begins.
- Instruct participant to report any subsequent event(s) that the participant, or the participant's physician, believes might reasonably be related to participation in this study.

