8.2.2 Relationship to Study Intervention

A clinician's assessment of an AE's relationship to study intervention is part of the documentation process, but it is not a factor in determining what is or is not reported in the study. If there is any doubt as to whether a clinical observation is an AE, the event should be reported. All AEs must have their relationship to study intervention assessed. In a clinical trial, the study intervention must always be suspect. The following guidelines are used for determination of relationship of any AE to the intervention or study procedures:

- **Related** – The AE is known to occur with the study intervention or study procedure, there is a reasonable possibility that the study intervention or procedure caused the AE, or there is a

CONFIDENTIAL

temporal relationship between the study intervention and event. Reasonable possibility means that there is evidence to suggest a causal relationship between the study intervention and the AE.

- **Not Related** – There is not a reasonable possibility that the administration of the study intervention or procedure caused the event, there is no temporal relationship between the study intervention or procedure and event onset, or an alternate etiology has been established.

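### The protocol records adverse events for 7 days (non-serious) or 30 days (serious) after the last visit, but for that period it asks participants for only the events believed to be related

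*Protocol*

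**What the plan says.** **Recording window.** Section 8.3 opens it at consent ("The PI will record all reportable events with start dates occurring any time after informed consent is obtained") and closes it "until 7 (for non-serious AEs) or 30 days (for SAEs) after the last day of study participation".

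**Role of relatedness.** Section 8.2.2 says of a clinician's causality assessment that "it is not a factor in determining what is or is not reported in the study". Section 8.3 reserves that assessment for people qualified to diagnose. Section 8.5 sends deaths and other SAEs to the monitoring team and sponsor whether or not they are related.

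**Collection.** Section 8.3 has the investigator ask about events at each study visit. Section 8.4.1 has AE forms completed at the three assessments and invites women to contact staff about any AE, but only while they are participating. Table A schedules AE assessment at TP1 and TP2, and nothing after TP2.

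**After the last visit.** Section 7.3.5 says: "Instruct participant to report any subsequent event(s) that the participant, or the participant's physician, believes might reasonably be related to participation in this study". Section 8.3 repeats it: "report any subsequent event(s) that the subject, or the subject's personal physician, believes might reasonably be related to participation in this study". Table A carries it as a single AE instruction entry at TP2.

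**The concern.** The recording rule and the instruction meant to supply it differ in scope. The rule covers a fixed period after TP2 and does not sort events by cause. The instruction covers an unlimited period after TP2 and does sort by cause, using the belief of the participant or her physician.

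Suppose a woman is admitted to hospital on day 15 after TP2 and neither she nor her physician connects it with MBSR or HEP. The event falls inside the 30-day window. If everyone follows the protocol exactly, she has not been asked to report it and no one is due to ask her.

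At stake is how the tail of the safety record can be read. Cumulative adverse event data go to the IRB and the funder each year (8.4.1). An empty 30-day tail could mean that nothing happened, or that nothing was thought related.

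**Working it through.** There is no planned statistic to reproduce. The check compares the rules with the schedule and then sizes the window.

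**Step 1. When does participation end?** Section 7.3.5 calls TP2 the final study visit, and section 5.5 counts participation as the three assessments plus the intervention. For a woman who completes the study, the last day is therefore TP2, and the window is TP2 + 7 days or TP2 + 30 days.

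**Step 2. What could bring an event in that window to the study?**

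| Route | Where | Reaches an event after TP2 that is thought unrelated? |
|---|---|---|
| Enquiry at study visits | 8.3, Table A | No; TP2 is the last visit |
| Open invitation to report any AE | 8.4.1 | No; limited to the time on study |
| Instruction given at TP2 | 7.3.5, 8.3, Table A | Not asked for; limited to events believed related |
| Presentation for medical care, or monitor review | 8.3 | Possibly, by chance; nothing is scheduled |
| SAE submission | 8.5 | Only once the site knows; the clock starts at awareness |

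No planned route solicits these events.

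**Step 3. Is the participant's belief a close stand-in for the protocol's own test?** No. Section 8.2.2 counts an event as related if there is merely a temporal relationship. A participant is likely to apply a narrower test, and she may apply it before anyone qualified under 8.3 has seen the event.

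**Step 4. How long is the window relative to the whole recording period?** Two lengths can be taken from the protocol.

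- *From the schedule, at its longest:* TP0 up to 3 weeks before the intervention, 8 weeks of intervention, three months (taken as 13 weeks) to TP2, plus the 1.5-week allowance. 3 + 8 + 13 + 1.5 = 25.5 weeks; 25.5 × 7 = 178.5 days. SAE tail: 30 / (178.5 + 30) = 30 / 208.5 = 14.4%. Non-serious tail: 7 / (178.5 + 7) = 7 / 185.5 = 3.8%.
- *From section 5.5:* approximately seven months, taken as 213 days. SAE tail: 30 / (213 + 30) = 30 / 243 = 12.3%. Non-serious tail: 7 / (213 + 7) = 7 / 220 = 3.2%.

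Both denominators are long ones. At the short limit (TP0 immediately before the intervention, TP2 1.5 weeks early), 8 + 13 − 1.5 = 19.5 weeks = 136.5 days, and 30 / 166.5 = 18.0%. These are shares of calendar time.

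**The case against.** **The instruction does not exclude other reports.** It tells women to report possibly related events; it does not tell them to withhold the rest. It has no time limit, so it can be read as a rule added to the fixed window. That reading is fair, but it does not supply a means of collecting unrelated events inside the window. The word *only* describes what is asked for, not a prohibition.

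**Reportable is undefined.** The rules in 8.3 and 8.4.1 that disregard cause are tied to the time on study, and 8.5 runs from site awareness, so a duty to seek unrelated events after TP2 is inferred. This stands as a caveat. But 8.5 takes SAEs whatever their cause, and 8.3 sets a separate fixed window, which would have little purpose beside the open-ended instruction if it held related events alone.

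**Little depends on it.** TP2 is about three months after the intervention, no formal safety analysis is planned (10.4.4), and no passage plans to interpret an empty tail. This stands, and it keeps the point minor. The data and safety monitoring plan and the manual of procedures are separate attachments and were not available; either might schedule a later contact.

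**Stronger readings that the documents do not support.** A reader might infer that the window also fails at its start. Section 8.3 says "Any medical condition that is present at the time that the participant is screened will be considered as baseline and not reported as an AE", while section 7.3.1 allows screening well before consent ("Recruitment (within three months of enrollment"). But 8.3 records only events that start after consent and collects time of onset, and medical history is taken at TP0 (7.3.2). A symptom that arose between screening and consent is excluded by its date, so no miscount follows. A reader might also infer that 8.2.2 forbids the participant's filter. Its sentence concerns a clinician's assessment; applying it to what participants volunteer extends its words.

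**Conclusion.** The concern holds for the end of the recording period. For up to 30 days after TP2 the protocol sets a recording rule wider than what it asks participants to report, and it schedules no contact that would close the gap. The period is about 12 to 14% of the SAE recording time on the two lengths that best match the protocol, and about 3 to 4% of the non-serious AE recording time. Neither figure estimates how many events would be missed: the documents give no event rates, and events believed related are still solicited throughout.

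This assumes that TP2 is the last day of participation, that reportable events after TP2 are not confined to related ones, and that the unseen attachments add no later contact. Severity is minor: at most 40 women, a study described as minimal risk, and no formal safety analysis. It is still worth correcting, because the change decides which events participants are asked to report.

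**What to change.** Reword the TP2 instruction in 7.3.5 and 8.3, so that the AE instruction row in Table A refers to the new text. Suggested wording:

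> At TP2, ask participants to tell study staff about any new or worsened condition that starts within 7 days, and any serious event (such as a hospital stay) that starts within 30 days, whatever they or their physician think caused it. After that, ask them to report any event that they or their physician think may be connected with the study.

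This leaves the recording window and the open-ended request for related events as they are.

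**Optional.** One automated prompt at day 30, using the contact details already held (5.4). With the rewording alone, silence still means that nothing was volunteered; a prompt with a reply would turn it into an answer. Women without REDCap access would need another route, and someone must read the replies.

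**Clean-up.** In the baseline sentence of 8.3, changing the reference point from screening to consent would match the start of recording. It corrects no miscount.

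**Cost.** A text amendment with IRB approval (13.2) and no extra visit. The downside is a few more unrelated reports, each needing assessment under 8.3 and, if serious, handling within the 8.5 deadlines.

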8.4 Reporting Procedures – Notifying the IRB

8.4.1 Adverse Event Reporting

AEs are not expected due to participation in this minimal risk study. However, AE forms will be completed at each of the three study assessments, and study participants will be encouraged to contact study staff immediately should any AEs occur during study participation. Periodic adverse event reporting will include any AE that occurs while a participant is on the research protocol, regardless of whether it is considered related to study participation.

The PI will submit as part of annual progress reports to the IRB and NINR a summary of monitoring that took place; cumulative adverse event data; assessments that were performed to evaluate external factors or relevant information that may have an impact on the safety of study participants or ethics of the research study; outcomes of procedural reviews conducted to ensure participant privacy and confidentiality; and final conclusions regarding changes to the anticipated risk-to-benefit ratio of study participants and recommendations related to continuing, changing, or terminating the study.

CONFIDENTIAL

8.4.2 Serious Adverse Event Reporting

SAEs are not expected due to participation in this minimal risk study. The procedure for AE reporting will be followed for SAEs. In addition, if a serious adverse event occurs, it will be reported in a timely fashion after adjudication: All SAE reports will be made to the IRB within 5 working days; any participant deaths will be reported to the NINR Program Officer within 24 hours of realization, and all other serious adverse events will be reported to NINR within 72 hours of realization.

8.4.3 Unanticipated Problem Reporting

UPs are not mentioned in the consent form or final study protocol; however, should UPs that are related to the intervention occur, the informed consent will be modified accordingly. The procedure for AE reporting will be followed for SAEs. In addition, if changes to the risk-to-benefit ratio of the study are determined based on occurrence of UPs, the IRB and NINR Program Officer will be notified.

Incidents or events that meet the OHRP criteria for UPs require the creation and completion of an UP report form. It is the PI's responsibility to report UPs to the IRB and to the NINR. The UP report will include the following information:

- Protocol identifying information: protocol title and number, PI's name, and the IRB project number;
- A detailed description of the event, incident, experience, or outcome;
- An explanation of the basis for determining that the event, incident, experience, or outcome represents an UP;
- A description of any changes to the protocol or other corrective actions that have been taken or are proposed in response to the UP.

To satisfy the requirement for prompt reporting, UPs will be reported using the following timeline:

- UPs that are SAEs will be reported to the IRB and to NINR within the timeframe described in 8.4.2 for SAEs.
- Any other UP will be reported to the IRB and to NINR within the timeframe described in 8.4.1 for AEs.
- All UPs should be reported to appropriate institutional officials (as required by an institution's written reporting procedures), the supporting agency head (or designee), and OHRP within the timeframe described for AEs or SAEs, as appropriate, after the IRB's receipt of the report of the UP from the investigator.

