8.1.3 Definition of Unanticipated Problems (UP)

Unanticipated Problems Involving Risk to Subjects or Others

Any incident, experience, or outcome that meets all of the following criteria:

- Unexpected in nature, severity, or frequency (i.e. not described in study-related documents such as the IRB-approved protocol or consent form, the investigators brochure, etc.)
- Related or possibly related to participation in the research (i.e. possibly related means there is a reasonable possibility that the incident experience, or outcome may have been caused by the procedures involved in the research)
- Suggests that the research places subjects or others at greater risk of harm (including physical, psychological, economic, or social harm).

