8.5 Reporting Procedures – Notifying the Study Sponsor

The study clinician will complete a SAE Form within the following timelines:

- All deaths and immediately life-threatening events, whether related or unrelated, will be recorded on the SAE Form and submitted to the data and safety monitoring team/study sponsor within 24 hours of site awareness. See Section 1, Key Roles for contact information.
- Other SAEs regardless of relationship will be submitted to the data and safety monitoring team /study sponsor within 72 hours of site awareness.

All SAEs will be followed until satisfactory resolution or until the site investigator deems the event to be chronic or the adherence to be stable. Other supporting documentation of the event may be requested by the data and safety monitoring team/study sponsor and should be provided as soon as possible.

As a follow-up to the initial report, within the following 48 hours of awareness of the event, the investigator shall provide further information, as applicable, on the unanticipated event or the unanticipated problem in

CONFIDENTIAL

the form of a written narrative. This should include a copy of the completed Unanticipated Problem form, and any other diagnostic information that will assist the understanding of the event. Significant new information on ongoing unanticipated adverse effects shall be provided promptly to the study sponsor.

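### Section 8.4.3 promises prompt reporting of unanticipated problems, but sends those that are not SAEs to a section whose only reporting interval to the IRB and NINR is annual

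*Protocol*

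**What the plan says.** Section 8.4.3 states the purpose of its timeline: "To satisfy the requirement for prompt reporting, UPs will be reported using the following timeline". Three bullets follow.

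- UPs that are also SAEs take the SAE timeframe in 8.4.2.
- For the rest, "Any other UP will be reported to the IRB and to NINR within the timeframe described in 8.4.1 for AEs".
- Onward reports to institutional officials, the agency head and OHRP take the AE or SAE timeframe, whichever applies, counted from the IRB's receipt of the investigator's report.

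Section 8.4.1, the target of the second bullet, contains one interval for reports to the IRB and NINR: "The PI will submit as part of annual progress reports to the IRB and NINR a summary of monitoring that took place", with cumulative adverse event data among the other contents of that report. It also says "AE forms will be completed at each of the three study assessments", which concerns data capture.

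Section 8.1.3 requires a UP to be unexpected, to be at least possibly related to the research, and to meet a third criterion: "Suggests that the research places subjects or others at greater risk of harm".

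**The concern.** A UP is by definition a signal of new or greater risk to participants or others. Section 8.4.3 recognises this by stating that its timeline serves prompt reporting, yet the cross-reference leads to an annual report. The rule defeats its own stated purpose for every UP that does not happen to be an SAE.

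At stake is the IRB's and the funder's ability to act in time. Section 5.7.3 lists unexpected or significant risk as grounds for suspension, and lets the study resume once concerns are addressed to the satisfaction of the sponsor and/or the IRB. That oversight depends on the IRB hearing of the problem. Participation lasts about seven months (section 5.5) and the intervention runs in successive cycles, so an annual report can arrive after the affected cycle has ended and another has begun.

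**Working it through.** No power, alpha or sample-size figure bears on this point. The check follows the cross-reference and then looks for any other deadline that would cover a non-SAE UP.

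**Step 1: the clocks to the IRB and NINR.**

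| Event | To the IRB | To NINR | Source |
|---|---|---|---|
| UP that is an SAE | 5 working days | 72 hours (death: 24 hours) | 8.4.3, pointing to 8.4.2 |
| UP that is not an SAE | AE timeframe: annual report | AE timeframe: annual report | 8.4.3, pointing to 8.4.1 |

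Section 8.4.1 also calls AE reporting periodic, without an interval, and encourages participants to contact staff at once. The first gives no deadline. The second concerns what reaches the study team, not what leaves it.

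**Step 2: longest delay.** A UP arising just after one annual report waits for the next, about 12 months. Taking a year as 365 days and 5 working days as about 7 calendar days:

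- IRB: 365 / 7 ≈ 52 times the interval for a UP that is an SAE.
- NINR: 365 / 3 ≈ 122 times the 72-hour interval.
- Against participation: for an event on a participant's first study day, 12 − 7 = 5 months could pass between the end of her participation and the report.

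**Step 3: onward reporting.** The third bullet starts the AE timeframe again at the IRB's receipt. Read literally, OHRP and institutional officials could wait 12 + 12 = 24 months.

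**Step 4: other provisions that touch UPs.**

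| Provision | What it does | Dated clock to the IRB and NINR for a non-SAE UP? |
|---|---|---|
| 8.4.3, risk-to-benefit notice | Notifies the IRB and the NINR Program Officer if UPs are determined to have changed the ratio | No; undated, and depends on that determination |
| 8.5, written narrative with UP form | "within the following 48 hours of awareness of the event, the investigator shall provide further information" | No; written for the sponsor, as a follow-up to an initial report that 8.5 defines only for SAEs |
| 10.6.3, group unblinding | Lets staff discuss with affected participants whether to continue | No; internal |
| 14.3, deviations | Reporting in 3 working days, including to NINR; IRB under its own guidelines | No; covers noncompliance only |
| 5.7.3 and 8.7, suspension | IRB informed promptly if the study is suspended or terminated | No; applies only once that decision is taken |
| 8.8, quarterly meeting | Team review | No; internal |

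No row supplies the missing deadline.

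**The case against.** The strongest reply is that the protocol would not in practice leave a real hazard unaddressed for a year. Section 10.6.3 provides for unblinding and discussion with participants when a UP could affect others. Section 8.4.3 itself calls for notice when the risk-to-benefit ratio changes. A UP caused by staff not following procedures may also be a deviation, with the 3-working-day rule in 14.3. The study is described as minimal risk. The data and safety monitoring plan and the manual of procedures, listed in section 19, may state a deadline. All of this stands, and it limits the point: the gap is in notice to the IRB and NINR, not in the study team's awareness or its ability to act. It does not remove the point, because none of these provisions gives non-SAE UPs a dated clock to those bodies, and 8.4.3 names 8.4.1 as the source of the timeframe.

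Three stronger readings are tempting, and the documents do not support them.

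- A reader might infer that a breach of genomic data would be a UP on the annual route. Section 2.3.1 already describes that risk, so under 8.1.3 it would be a UP only if its severity or frequency were unexpected. It may also be a deviation under 14.3.
- A reader might set the 48 hours in 8.5 against the 12 months as rival deadlines for the same event. The 8.5 clause has a different recipient, and it is not clear that it covers non-SAE UPs at all.
- A reader might see a contradiction for life-threatening SAEs. Section 8.5 says "All deaths and immediately life-threatening events, whether related or unrelated, will be recorded on the SAE Form" and gives 24 hours for submission. Section 8.4.2 gives 24 hours for deaths, but "all other serious adverse events will be reported to NINR within 72 hours of realization". The first clock runs to the monitoring team and sponsor, the second to NINR, and both can be met together. A conflict arises only if the sponsor is NINR. The public text does not settle that: section 15.1 names NINR as funder.

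**Conclusion.** The defect is real and narrow. For UPs that are not SAEs, the protocol's own cross-reference produces an annual report to the IRB and NINR, which contradicts the stated aim of prompt reporting. The longest delay is about 12 months, and about 24 months for OHRP and institutional officials if the third bullet is read literally.

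This rests on two assumptions: that the annual progress report is the timeframe meant by the pointer to 8.4.1, since that section contains no other reporting interval to these bodies; and that no attached plan or manual overrides it. It is a safety-reporting error in the wording, with no effect on the sample size, the endpoints or the analysis.

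**What to change.** In 8.4.3, replace the pointer to 8.4.1 with an explicit prompt timeframe for UPs that are not SAEs, agreed with the IRB and NINR. Change the matching AE reference in the third bullet in the same way. If the data and safety monitoring plan or the manual already holds a deadline, bring it into 8.4.3.

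Reconcile the result with the UP narrative clause in 8.5, and state there whether that clause covers non-SAE UPs and what initial report it follows. The sentence in the first paragraph of 8.4.3 that applies the AE procedure to SAEs sits under the UP heading and should be checked in the same edit.

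As a clarification only, 8.4.2 and 8.5 should say whether the sponsor and NINR are the same recipient.

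The cost is a protocol amendment to wording, with IRB review. No procedure, visit or analysis changes.
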